4.11.5 EORTC QLQ-C30

Observed values and change from baseline of the standardised function scales, symptom scales, global health status scale and standardised single item scales will be summarised at each applicable study visit.

The proportion of patients with no adverse change in the global health status scale will be summarised for each 3-month time period since the start of the study.

4.11.6 EQ-5D-5L

Observed values and change from baseline of the EQ-5D-5L Crosswalk normalised score will be summarised at each applicable study visit.

The proportion of patients with no adverse change in the normalised score will be summarised for each 3-month time period since the start of the study.

4.11.7 FACIT-F

Observed values and change from baseline of the FACT-G Total Score, FACIT-F Total Score and FACIT-F Trial Outcome Index will be summarised at each applicable study visit.

The proportion of patients with no adverse change in the FACIT-F Total Score will be summarised for each 3-month time period since the start of the study.

4.12 Analysis of Safety

All presentations and analyses of safety data will be conducted on the FAS. All safety data will be listed.

4.12.1 Adverse Events

A summary overview of adverse events will be provided, which presents the number and percentage of patients from the FAS satisfying each of the following categories:

- Any AEs
- Serious AEs (SAEs)
- Drug-related AEs
- SAEs leading to death
- AEs leading to discontinuation

The number and percentage of patients with AEs, and number of AEs will be summarised by MedDRA System Organ Class, High Level Term, and Preferred Term. In this summary, any patient reporting multiple episodes of the same AE (i.e. same preferred term), will be counted once. The incidence of SAE will also be summarised. The listings will contain all data available.

The number and percentage of patients with AEs will be summarised by reported severity within each preferred term within system organ class. In this summary, any patients reporting multiple episodes of the same AE (i.e. same preferred term), will be counted once against the most severely reported category.

A list of patients reporting any SAEs and a list of patients reporting any AEs that led to an interruption or withdrawal of the study medication will be provided.

4.12.2 Clinical Laboratory Assessments

Observed values and change from baseline will be summarised at each applicable study visit for the parameters listed in Section 3.3.4. Counts and percentages of patients in each category will be used to summarise categorical urinalysis parameters for the baseline visit and each post-baseline assessment.

Counts and percentages of patients with haematology and chemistry observations that are below (<LLN) or above (>ULN) the limit of normal at any post baseline visit will be summarised. Patients with haematology or chemistry observations that are below (<LLN) or above (>ULN) the limit of normal at *any* post baseline visit will be listed, as well as patients with markedly abnormal values.

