1.1. PNH

PNH is an acquired genetic haemolytic anaemia, in which failure to synthesise GPI-anchored proteins prevents affected blood cells from attaching the complement regulatory proteins CD55 and CD59 to their surface, making them vulnerable to attack by normal background complement activity. The resulting intravascular haemolysis of affected red blood cells (RBC) causes free haemoglobin to be released into the bloodstream. Some lysis of RBC may also be extravascular caused by complement deposition on cell surfaces and subsequent phagocytosis via the reticulo-endothelial system, in particular Kupfer cells and splenic phagocytes [Brodsky et al, 2014]. In the bloodstream, free haemoglobin causes depletion of nitric oxide with resultant smooth muscle spasm causing or contributing to symptoms such as dysphagia, erectile dysfunction, abdominal pain and, possibly, pulmonary hypertension.

PNH is characterised by red blood cell haemolysis, large vessel thrombosis particularly affecting the hepatic, visceral, cerebral and dermal veins and impaired haematopoiesis. The relationship between aplastic anaemia and PNH is not fully understood, however there is a greater incidence of PNH in patients with a history of aplastic anaemia, possibly because PNH clones have a higher rate of proliferation in this condition than normal stem cells. Treatment of aplastic anaemia with immunosuppressants is known to increase PNH clone size but whether the cells so produced are more or less susceptible to haemolysis than other PNH cells remains controversial. PNH patients with bone marrow aplasia are more likely to require blood transfusion because of the impaired production of normal red cells.

Treatment of PNH is by bone marrow allograft or, where available, by terminal complement blockade with the only approved complement C5 inhibitor, the monoclonal antibody eculizumab. Untreated, patients with PNH have a reduced life expectancy, principally because of major thrombotic events. Side effects of repeated blood transfusion, such as iron accumulation, also contribute to the morbidity of the disease.

1.2. aHUS

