2.4 Study Endpoints

2.4.1 Primary Endpoint

Long term safety of rVA576 (Coversin) therapy as assessed by AEs, serious adverse events (SAEs), vital signs, results of standard laboratory tests (clinical chemistry, haematology and urinalysis), and results of electrocardiograms (ECGs).

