3.4.7 ECG

Routine ECG will be performed at entry and then annually during the study. The following ECG parameters will be recorded in the eCRF:

- Heart rate (beats/min)
- PR interval (msec)

- QRS duration (msec)
- QT interval (msec)
- QTc interval (msec)
- RR interval (msec)
- Overall interpretation

Interpretation of the ECG will be performed by the investigator and reported as normal, abnormal, inderminate, and if deemed abnormal, whether the abnormality is clinically significant or not clinically significant.

Changes in each ECG parameter from Baseline or any additional unscheduled ECGs, will be derived.

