4.12.4 Electrocardiogram

The number and percentage of patients who have an ECG post-baseline Overall interpretation that falls within each category ('Normal'; 'Abnormal, Not Clinically Significant'; 'Abnormal, Clinically Significant') will be tabulated.

Observed values and change from baseline of ECG measurements will be summarised at each applicable study visit.

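### The only laboratory safety count in SAP 4.12.2 flags any out-of-range value at any post-baseline visit, so it mixes entry abnormality, length of follow-up and new change; a shift from entry is needed

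*SAP*

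**What the plan says.** SAP 2.4.1 names standard laboratory tests and ECGs among the components of the primary safety endpoint. SAP 4.12.2 then plans four laboratory outputs:

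- Continuous summaries: "Observed values and change from baseline will be summarised at each applicable study visit for the parameters listed in Section 3.3.4". The cross-reference is wrong. SAP 3.3.4 is the EORTC QLQ-C30 section, and the laboratory parameters are in 3.4.4.
- Urinalysis: "Counts and percentages of patients in each category will be used to summarise categorical urinalysis parameters for the baseline visit and each post-baseline assessment".
- Haematology and chemistry counts and percentages of patients: "observations that are below (<LLN) or above (>ULN) the limit of normal at any post baseline visit will be summarised". Nothing is said about entry status, degree, persistence or follow-up.
- Listings: patients outside the normal range "will be listed, as well as patients with markedly abnormal values". The SAP gives no limits for the latter.

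Appendix 7.1 has tables of observed values and change from baseline (14.3.2.1 to 14.3.2.3), but no shift table and no table for the out-of-range count. Out-of-range listings appear in Appendix 7.2.

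For ECG, SAP 4.12.4 tabulates "The number and percentage of patients who have an ECG post-baseline Overall interpretation that falls within each category", with three categories: normal, and abnormal with or without clinical significance. SAP 3.4.7 says the interpretation is "reported as normal, abnormal, inderminate", which allows a result with no place in that table. Table 14.3.4.2 is by visit, and ECGs are annual.

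**The concern.** The study has no control arm, so a patient's own entry value is the main reference available for judging a later laboratory result. The any-visit count discards it. A patient already out of range at entry who stays there counts the same as one who was normal and became abnormal. A patient followed for four years has many more chances of a stray flag than one who leaves after three months.

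This also sits badly with the documents' own logic. Protocol 7.2.2 treats a laboratory abnormality present at baseline as pre-existing, to be recorded as an adverse event only if it worsens. Protocol 1.1 says "PNH is an acquired genetic haemolytic anaemia", so some red-cell and haemolysis flags are to be expected from the disease. SAP 4.11.2 puts LDH up to 1.8 times ULN in its lowest efficacy band, so a patient at 1.5 times ULN is in the best efficacy band and is still flagged as abnormal for safety.

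At stake is whether the reported percentage can be read as new laboratory abnormality arising during long-term treatment. As defined, it cannot.

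**Working it through.** The plan states no abnormality rate, so there is no figure of its own to reproduce. The check asks how far the count moves when nothing changes except the number of visits or the entry level.

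**Inputs from the documents.** Protocol Tables 8 and 9 schedule haematology and chemistry at months 1, 2, 3, 6 and then every 3 months to 48. That is 18 post-entry visits, plus early termination and any unscheduled visits. It is 3 visits by month 3, 4 by month 6 and 14 by month 36. SAP 4.9 has exposure bands from 1–182 days (about 4 visits) up to 731–1095 days (up to about 14).

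**Assumptions, not in the documents.** The normal range covers 95% of values in an unaffected patient (limits at ±1.96 SD). Within-patient correlation ρ runs from 0 to 0.9. There is no drug effect.

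**Formula.** Independent visits: P(flagged over k visits) = 1 − 0.95^k. For k = 18 this is 1 − 0.95^18 = 0.603, and for k = 3 it is 1 − 0.95^3 = 0.143. Correlated visits: write each value as √ρ·u + √(1−ρ)·e, with u fixed per patient and u and e standard normal. Then P = 1 − E_u{[Φ((1.96−√ρ·u)/√(1−ρ)) − Φ((−1.96−√ρ·u)/√(1−ρ))]^k}.

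One parameter, either side of the range:

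| Visits | ρ=0 | 0.3 | 0.5 | 0.7 | 0.9 |
|---|---|---|---|---|---|
| 3 | 14% | 14% | 13% | 11% | 8% |
| 4 | 19% | 17% | 16% | 13% | 9% |
| 14 | 51% | 44% | 35% | 25% | 14% |
| 18 | 60% | 51% | 40% | 28% | 15% |

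The percentage rises with follow-up at every correlation.

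**Markers raised at entry.** Suppose a marker is centred 2 SD above the middle of the range, so that about 51% are high at entry. Over 18 visits the count above ULN is 95%, 88% and 74% at ρ = 0.5, 0.7 and 0.9, with no drug effect. These are illustrations, because the documents do not give entry rates.

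**Does the count still respond to a real change?** Add a +1 SD shift after entry, over 18 visits. For a parameter centred in the range, the count above ULN goes from 20% to 66% (ρ = 0.5) or from 14% to 52% (ρ = 0.7). For the raised marker it goes from 95% to 99.8% or from 88% to 99%, so little room is left.

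**What an entry restriction does alone.** Among patients in range at entry, the 18-visit figures of 60%, 40%, 28% and 15% (ρ = 0, 0.5, 0.7, 0.9) become 60%, 38%, 25% and 11%. The restriction removes pre-existing abnormality but barely touches accumulation over visits. A by-visit column does not accumulate: under these assumptions it stays at or below 5% at each visit, whatever the follow-up.

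**ECG.** There are at most four scheduled post-entry readings (months 12, 24, 36, 48), tabulated one visit at a time, so this accumulation does not arise.

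**The case against.** The strongest case on the other side is that the any-visit count is one summary among several. Observed values and change from baseline are tabulated by visit. Urinalysis categories are shown at baseline and at each visit. LDH has its own bands by 3-month period and a per-patient median (SAP 4.11.2), and haemoglobin is compared with the parent-trial baseline (4.11.3). Under Protocol 7.1.1 and 7.2.2, new or worsening laboratory findings can be recorded as adverse events, which SAP 4.12.1 tabulates by severity. All safety data are listed for at most about 50 patients. A new signal thus has other routes to view. All of this stands, and it limits the consequence. It does not supply the missing figure, which is how many patients went from normal to abnormal on each parameter.

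Three stronger readings are tempting, and the documents do not support them.

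- *A reader might infer that laboratory safety saturates.* A single normal-range parameter reaches 15% to 60% over 18 visits and still responds to a shift. Near-saturation applies to markers already raised at entry, or to a count pooled over all 34 listed parameters (1 − 0.95^34 = 82% at a single visit if parameters were independent, which related red-cell indices are not). The SAP does not say that it pools. Also, 18 visits applies only to a 48-month completer.
- *A reader might infer that this rule is why no drug effect can be shown.* The main reasons are the single-arm design, the purely descriptive analysis, and a baseline taken when patients have already been treated (SAP 3.1). Shift tables change none of these.
- *A reader might infer that ECG has the same flaw.* It is annual, tabulated by visit, includes a normal category, and has numeric change from baseline. Only the entry comparison and the indeterminate category are missing.

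**Conclusion.** The point holds for the haematology and chemistry count in SAP 4.12.2. As defined, it cannot separate abnormality present at entry, number of visits and new change. Under the assumed 5% rate with no drug effect, going from 3 to 18 visits moves one parameter from 14% to 60% if visits are independent, and from 8% to 15% at correlation 0.9. The direction does not depend on the correlation; the size does. The position of haemolysis markers near the ceiling is plausible but not quantified by the documents, since patients enter on treatment and entry rates are not reported. The undefined markedly abnormal limits may be set in the stand-alone programming specification (SAP section 6), which is not among the documents. This is a worthwhile and inexpensive improvement to one part of the safety reporting. It does not show that the primary endpoint fails.

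**What to change.** In SAP 4.12.2 and Appendix 7.1:

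- For each haematology and chemistry parameter, replace or supplement the any-visit count with shift tables from entry category (low, normal, high) to the category at each scheduled visit and to the worst post-entry category. The by-visit columns are essential, because entry-to-worst still grows with follow-up.
- Report new abnormalities only among patients not already abnormal in that direction at entry, and show the number of visits or patient-years alongside.
- State that counts are per parameter. Give the limits for markedly abnormal values, or point to where they are set. Correct the cross-reference from 3.3.4 to 3.4.4.

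In SAP 4.12.4, add an entry-to-visit shift of the overall ECG interpretation, with an indeterminate category to match 3.4.7.

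The cost is SAP wording and a few more standard tables. All the data are already scheduled for collection.

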4.12.3 Vital Signs

Observed values and change from baseline of Vitals signs measurements will be summarised at each applicable study visit.

Subjects with markedly abnormal values for vital signs will be listed.

4.12.4 Electrocardiogram

The number and percentage of patients who have an ECG post-baseline Overall interpretation that falls within each category ('Normal'; 'Abnormal, Not Clinically Significant'; 'Abnormal, Clinically Significant') will be tabulated.

Observed values and change from baseline of ECG measurements will be summarised at each applicable study visit.

4.12.5 Thrombotic and Haemolytic Events

The number and percentage of patients

- i) without a thrombotic event,
- ii) without a haemolytic event,
- iii) without either a thrombotic or haemolytic event,

will be summarized at each visit. The time (days) to first event for each patient will be summarized using Kaplan-Meier methodology. Kaplan-Meier estimates of the proportion of patients achieving each event during the study will be displayed with 95% two-sided

confidence limits. The median, 95% Confidence Interval of the median, 25th and 75th percentiles of the time to achieving event will be produced.

4.12.6 Major Adverse Vascular Event (MAVE)

The number and percentage of patients with MAVEs, and number of MAVEs will be summarised by MedDRA System Organ Class, High Level Term, and Preferred Term. In this summary, any patient reporting multiple episodes of the same MAVE (i.e. same preferred term), will be counted once. The listings will contain all data available.

The time (days) to first MAVE for each patient will be summarized using Kaplan-Meier methodology. Kaplan-Meier estimates of the proportion of patients experiencing MAVE events during the study will be displayed with 95% two-sided confidence limits. The median, 95% Confidence Interval of the median, 25th and 75th percentiles of the time to experiencing event will be produced.

4.13 Interim Analysis

The Sponsor reserves the right to review accruing safety and efficacy data from the study as a management aid to assist in the design of future studies.

4.14 Data Safety Monitoring Board (DSMB)

Not applicable

5 Sample Size Determination

This is an open-label study to evaluate the safety experience of long term rVA576 (Coversin) treatment in up to approximately 50 patients.

6 Programming Specifications

The programming specification, including the mock-up analysis tables, figures, and data listings, as well as the derived database specification, will be prepared in a stand-alone documents.

7 APPENDIX 1

7.1 Tables

Table 14.1.1	Patient Disposition – Screened Set
Table 14.1.2	Demographics and Baseline Characteristics – Full Analysis Set
Table 14.1.3	Medical History –Full Analysis Set
Table 14.1.4	Concomitant Medication by ATC and preferred term – Full Analysis Set
Table 14.1.5	Transfusions and Complement Inhibitor history Subgroup – Full Analysis Set
Table 14.2.1.1	Incidence of PRBC transfusions by timeperiod and overall – Full Analysis Set
Table 14.2.1.1	Incidence of PRBC transfusions by timeperiod and overall by Subgroups – Full Analysis Set
Table 14.2.1.2	Time to first PRBC transfusion – Full Analysis Set
Table 14.2.1.3	Number of transfusions – Full Analysis Set
Table 14.2.1.4	Summary of Transfusion-independence – Full Analysis Set
Table 14.2.2.1	EORTC QLQ-C30 by visit: observed values and change from baseline – Full Analysis Set
Table 14.2.2.1	Summary of EORTC QLQ-C30 adverse changes at each 3 month period – Full Analysis Set
Table 14.2.2.2	EQ-5D-5L by visit: observed values and change from baseline – Full Analysis Set
Table 14.2.2.2	Summary of EQ-5D-5L adverse changes at each 3 month period – Full Analysis Set
Table 14.2.1.3	FACIT-F by visit: observed values and change from baseline – Full Analysis Set
Table 14.2.1.3	Summary of FACIT-F adverse changes at each 3 month period – Full Analysis Set
Table 14.2.2.1	Serum LDH by visit: observed values and change from baseline – Full Analysis Set
Table 14.2.2.2	Summary of Serum LDH levels at each 3-month time period – Full Analysis Set
Table 14.2.2.3	Summary of median Serum LDH levels – Full Analysis Set
Table 14.2.3.1	Summary of Transfusion-independence and Haemoglobin at each 3-month time period – Full Analysis Set
Table 14.2.3.2	Summary of Transfusion-independence and Haemoglobin at each month time period by Subgroups – Full Analysis Set
Table 14.2.3.3	Summary of Transfusion-independence and mean Haemoglobin – Full Analysis Set
Table 14.2.3.4	Summary of Transfusion-independence and mean Haemoglobin by Subgroups – Full Analysis Set

Table 14.3.1.1	Summary overview of AEs – Full Analysis Set
Table 14.3.1.2	AEs – Full Analysis Set
Table 14.3.1.3	AEs by maximum severity – Full Analysis Set
Table 14.3.1.4	Serious AEs – Full Analysis Set
Table 14.3.2.1	Haematology parameters by visit: observed values and change from baseline – Full Analysis Set
Table 14.3.2.2	Chemistry parameters by visit: observed values and change from baseline – Full Analysis Set
Table 14.3.2.3	Urinalysis parameters by visit: observed values and change from baseline – Full Analysis Set
Table 14.3.2.4	Categorical Urinalysis parameters by visit: observed values – Full Analysis Set
Table 14.3.3	Vital signs by visit: observed values and change from baseline – Full Analysis Set
Table 14.3.4.1	Electrocardiogram by visit: observed values and change from baseline – Full Analysis Set
Table 14.3.4.2	Electrocardiogram by visit: overall interpretation – Full Analysis Set
Table 14.3.5.1	Thrombotic Events – Full Analysis Set
Table 14.3.5.2	Haemolytic Events – Full Analysis Set
Table 14.3.5.3	Time to first Thrombotic Events – Full Analysis Set
Table 14.3.5.4	Time to first Haemolytic Events – Full Analysis Set
Table 14.3.5.5	Time to first Thrombotic or Haemolytic Events – Full Analysis Set
Table 14.3.6.1	Major Adverse Vascular Events – Full Analysis Set
Table 14.3.6.2	Time to first MAVE – Full Analysis Set
Table 14.3.7	Study drug exposure and compliance – Full Analysis Set
Table 14.4.1.1	CH50 by visit: observed value and change from baseline – Full Analysis Set
Table 14.4.1.2	CH50 by visit: observed value and percentage activity – Full Analysis Set
Table 14.4.2.1	Unbound nomacopan, total C5 and serum LTB4 levels – Full Analysis Set

7.2 Listings

- Listing 16.2.1.1 Patient Disposition
- Listing 16.2.1.2 Screen failures and screen failure reasons
- Listing 16.2.1.3 Visit dates
- Listing 16.2.2 Protocol deviations
- Listing 16.2.3 Exclusion from the analysis populations

- Listing 16.2.4.1 Demographic Data
- Listing 16.2.4.2 Eligibility Criteria
- Listing 16.2.4.3 Medical History
- Listing 16.2.4.4 Childbearing potential
- Listing 16.2.4.5 Serum Pregnancy Test
- Listing 16.2.4.6 Concomitant Medication

- Listing 16.2.5.1 Exposure and Compliance
- Listing 16.2.5.2 Drug Accountability

- Listing 16.2.6.1 Transfusions
- Listing 16.2.6.2 EORTC QLQ-C30 legend
- Listing 16.2.6.3 EORTC QLQ-C30
- Listing 16.2.6.4 EQ-5D-5L legend
- Listing 16.2.6.5 EQ-5D-5L
- Listing 16.2.6.6 FACIT-F legend
- Listing 16.2.6.7 FACIT-F
- Listing 16.2.6.8 Self-Injection Questionnaire

- Listing 16.2.7.1 Adverse events
- Listing 16.2.7.2 Serious adverse events
- Listing 16.2.7.3 Adverse events leading to discontinuation or leading to death

- Listing 16.2.8.1.1 Haematology
- Listing 16.2.8.1.2 Haematology – out of normal range and markedly abnormal values
- Listing 16.2.8.2.1 Chemistry
- Listing 16.2.8.2.2 Chemistry – out of normal range and markedly abnormal values
- Listing 16.2.8.3.1 Urinalysis
- Listing 16.2.8.3.2 Urinalysis – out of normal range and markedly abnormal values

- Listing 16.2.9.1 Vital Signs
- Listing 16.2.9.2 Electrocardiogram

- Listing 16.2.10.1 Thrombotic and Haemolytic Events
- Listing 16.2.10.2 Major Adverse Vascular Events

- Listing 16.2.10.1 CH50
- Listing 16.2.10.2 ADA sampling
- Listing 16.2.10.3 PK sampling
- Listing 16.2.10.4 Fluorescein-labelled proaerolysin FLAER / Flow Cytometry

Listing 16.2.10.5 Physical Examinations abnormalities

Listing 16.2.10.6 Neisseria Meningitidis Immunisation History

7.3 Figures

Figure 14.2.1 Line plot of derived LDH ratio over time

Figure 14.2.2 Boxplots of LDH ratio over time

Figure 14.4.1 Line plot of Unbound nomacopan over time

Figure 14.4.2 Line plot of total C5 over time

Figure 14.4.3 Line plot of serum LTB4 over time
